13.2 Secondary Endpoints

1. Days alive and out of hospital at 6 months, not listed for transplant (status 1A, 1B or 1-4) or undergoing transplant, implanted with an LVAD, maintained or started on continuous inotropic therapy for ≥ 7 days, or has had two hospital admissions for HF (other than the index admission*). If a patient meets the pre-specified secondary endpoint of 2 hospital admissions for heart failure (other than the index admission), the patient can remain on study drug or be started on open label sacubitril/valsartan, at the treating physician's discretion, while remaining in the trial.

*The days alive and out of hospital will end on the day of the second readmission.

2. Tolerability measured as:
 - a) Number of subjects achieving a target dose of 25%, 50% or 100% of valsartan or LCZ696
 - b) Number of subjects developing hypotension (SBP ≤ 85 mmHg) with symptoms
 - c) Number of subjects developing worsening renal function (eGFR < 20 ml/min/1.73 m²)
 - d) Number of subjects developing moderate (≥ 5.5 mmol/L) or severe (≥ 6 mmol/L) hyperkalemia

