## 10. Secondary Endpoint Descriptions

### 10.1 – Secondary Endpoint #1

Endpoint Description: Days alive and out of hospital at 24 weeks, not listed for transplant (Status 1A, 1B or 1-4) or undergoing transplant, implanted with an LVAD, maintained or started on continuous inotropic therapy for  $\geq 7$  days, or has had two hospital admissions for heart failure (HF), other than the index admission. The days alive and out of hospital will end on the day of the second HF readmission, if applicable, using the pre-COVID-19 population.

Response Variable Definition: Each component of the endpoint will have daily flags created indicating whether the patient met the endpoint on that specific day. Days will start at day of randomization (Day 0) and continue until a maximum of 163 (beginning of 24 week visit window). Determination of the final evaluable date will depend upon which component is under evaluation. Any data collected after 163 days post randomization will not count for this endpoint.

Days alive: If a patient died between randomization and 163 days post randomization, each day will be coded as a 0 if they were alive and will be coded as a 1 if the patient has previously died. All 163 post-randomization days will be evaluable if the patient died. If the patient had not died, the last evaluable date will be minimum of 163 days post randomization, date of Week 24 visit, date of withdrawn consent or date of loss to follow-up.

Out of hospital: If a patient was randomized while admitted to the hospital, each day the patient was in the hospital from randomization to discharge will be coded as a 1, otherwise the coded value will be a 0. For every other unplanned hospital admission, the patient will be coded as a 0 if they were not hospitalized and coded as a 1 if they were, using the admission and discharge dates as the anchors. The last evaluable date will be minimum of 163 days post randomization, date of Week 24 visit, date of withdrawn consent, date of death or date of loss to follow-up.

Not listed for transplant or undergoing transplant: If a patient either has been listed for heart transplant or received a transplant, each day will be coded as a 0 if they were not listed/transplanted and will be coded as a 1 if the patient had been listed or transplanted. The last evaluable date will be minimum of 163 days post randomization, date of Week 24 visit, date of withdrawn consent, date of death or date of loss to follow-up.

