Not implanted with a LVAD: If a patient had been implanted with a LVAD, each day will be coded as a 0 if they were not implanted and will be coded as a 1 if the patient had been implanted. The last evaluable date will be minimum of 163 days post randomization, date of Week 24 visit, date of withdrawn consent, date of death or date of loss to follow-up.

Not maintained or starting continuous IV inotropes for at least 7 days: If the patient had been taking continuous IV inotropes for at least 7 days, each day from the start of inotropes (or randomization date if inotropes started prior to randomization) through the discontinuation of inotropes will be coded as a 1. If the patient does not have a discontinuation date, the assumption will be that inotropes continued to minimum of 163 days post randomization, date of Week 24 visit, date of withdrawn

consent, date of death, or date of loss to follow-up. For those days where the patient is not taking inotropes, the coded value will be 0.

Free of two heart failure hospitalizations: If the patient had two unplanned heart failure hospitalizations, each day from the second HF admission will be coded as a 1. Every day prior to the second HF admission will be coded as a 0. Coding will continue through a minimum of 163 days post randomization, date of Week 24 visit, date of withdrawn consent, date of death, or date of loss to follow-up.

Composite endpoint of event free days: Using each of the endpoint components above, determine the maximum value for the coded value for each of Day 0 through 163. If no endpoints met, the patient met the criteria for an event free day.

Additional Covariates in Addition to Randomized Treatment: atrial fibrillation status at time of randomization

Handling of Dropouts and Missing Data: To account for missing data due to right censoring, inverse probability weighted estimates will be calculated for each treatment group. These estimators adjust for the potential bias due to administratively censored data by reweighting the observed data by a function of the Kaplan-Meier estimate of the censoring distribution. The data will be partitioned from randomization (Day 0) to Day 79 and Day 80 to Day 163.

Sensitivity Analyses:

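### SAP 10.1 censors patients at withdrawal or loss even after a permanent non-fatal event (transplant or listing, LVAD, second HF admission), when the remaining event-free days are already known to be zero

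*SAP*

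**What the plan says.** SAP 10.1 builds daily flags for each component from Day 0 to Day 163, and "Determination of the final evaluable date will depend upon which component is under evaluation".

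- **Death:** "All 163 post-randomization days will be evaluable if the patient died". Every day after death is coded 1.
- **Transplant or listing:** one component; each day "will be coded as a 1 if the patient had been listed or transplanted". The last evaluable date is the earliest of Day 163 and "date of Week 24 visit, date of withdrawn consent, date of death or date of loss to follow-up".
- **LVAD:** coded 1 once implanted, with the same last evaluable date.
- **Second HF admission:** coded 1 from the second admission, but "Coding will continue through a minimum of 163 days post randomization, date of Week 24 visit, date of withdrawn consent", death or loss to follow-up.
- **Hospital days and inotropes:** coded 1 only while they last.

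Protocol 13.2 says of the same endpoint: "The days alive and out of hospital will end on the day of the second readmission". SAP 10.1 repeats this in its endpoint description.

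Incomplete follow-up is handled by a partitioned Bang-Tsiatis estimator (Days 0-79 and 80-163), "reweighting the observed data by a function of the Kaplan-Meier estimate of the censoring distribution". The SAP describes the censoring it has in mind as administrative. The three sensitivity analyses change the cut-off days or the population, and none changes the evaluability rule.

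**The concern.** After death the SAP knows that no later day can be event-free, so it keeps the patient complete to Day 163. The same is true after any other component that is coded 1 permanently. For the second HF admission it holds by definition, because the count ends that day. Yet a patient who has such an event and then withdraws or is lost has no coded days after leaving, and so enters the weighting step as censored.

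Take an LVAD on Day 60 and withdrawal on Day 75. The outcome is fully known (60 event-free days), but the patient is incomplete for both partitions and gets zero weight in both. Patients still in follow-up stand in for this one.

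Kaplan-Meier weights computed within arm need dropout to be unrelated to outcome. The present rule asks for that assumption even after a permanent event, where it is not needed and is least secure. If it fails there, patients with poor outcomes are under-represented and mean event-free days are overstated.

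**Working it through.** **No plan figure to reproduce.** The documents give no expected mean, SD, event rate or power for this endpoint. The day limits do reproduce: 24 × 7 − 5 = 163 and 12 × 7 − 5 = 79.

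**Inputs from the documents:** horizon Day 163; cuts at Days 79 and 163; dropout or withdrawal about 5% (protocol 16.2); 335 patients in the pre-COVID-19 population, about 168 per arm, of whom 25 (7.5%) lose some visit data to the March 1, 2020 cut (SAP section 3).

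**Assumptions, not in the documents:** 12% dead by Day 163; 10%, 20% or 30% reaching a permanent non-fatal state; constant hazards; total dropout 5%, with 10% as a range; dropout hazard after the event 1, 3, 5 or 10 times that before it (HR).

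**Estimator.** In each arm, with T the time at which a patient counts as complete, C the dropout time, K the Kaplan-Meier estimate of remaining uncensored, and t_j the partition limits:

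mean = Σ_j (1/n) Σ_i 1[C_i ≥ min(T_i, t_j)] × Y_ij / K(min(T_i, t_j)),

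where Y_ij is the number of event-free days in partition j. Under the SAP rule, T is the earlier of death and Day 163. Under the fix, T is the earliest of death, permanent event and Day 163.

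**True mean.** With 20% events and 12% deaths, λ × 163 = −ln(0.80) − ln(0.88) = 0.223 + 0.128 = 0.351, so the mean is 163 × (1 − e^(−0.351)) / 0.351 ≈ 137.5 days. With 14% events the sum is 0.279 and the mean about 142.3. The true difference is about 4.8 days.

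**Step 1. Dropout unrelated to the event (HR 1).** SAP-rule bias is 0.00 days (within ±0.01) at 5% and at 10% dropout. With the calendar cut alone, the truth is 137.43, the SAP rule gives 137.42 and the fix 137.43. At 168 per arm the SD of an arm mean is 3.70 under the SAP rule and 3.65 under the fix, a loss of about 1%.

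**Step 2. Dropout more likely after the event.** Overstatement of an arm's mean under the SAP rule, in days:

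| Permanent event by Day 163 | Dropout | HR 3 | HR 5 | HR 10 |
|---|---|---|---|---|
| 10% | 5% | 0.38 | 0.67 | 1.21 |
| 20% | 5% | 0.64 | 1.08 | 1.79 |
| 30% | 5% | 0.85 | 1.34 | 2.05 |
| 10% | 10% | 0.75 | 1.30 | 2.32 |
| 20% | 10% | 1.30 | 2.21 | 3.54 |
| 30% | 10% | 1.70 | 2.73 | 4.19 |

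The fix is unbiased to within 0.01 days in every row. If every one of the 5% dropouts left directly after an event, the overstatement would be 3.2 to 3.9 days.

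**Step 3. A true difference (20% vs 14% events).** With the same dropout hazards in both arms, set to give 5% dropout in the control arm, the difference shrinks by about 3.5%, 6.5% and 10% at HR 3, 5 and 10. With 10% dropout the figures are 8%, 13% and 21%. If total dropout is instead held at 5% in each arm (with 10% mortality), the loss is 0.15, 0.22 or 0.28 days of about 4.9, or 3% to 6%. A repeat simulation agreed to within about one percentage point.

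**Step 4. No true effect (20% events in both arms).** At 5% dropout:

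- HR 5 in both arms: mean difference 0.07 days, which is simulation noise.
- HR 5 in one arm only: 1.1 days, against a standard error of 5.26; false-positive rate 5.1%.
- HR 10 in one arm only: 1.9 days; false-positive rate 6.2%.

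At 10% dropout with HR 10 in one arm only, the difference is 3.6 days and the false-positive rate 10.7%.

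**Step 5. Partitions.** A patient lost after Day 79 still contributes Days 0-79 and loses only the second partition.

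**The case against.** A reader might infer that the rule by itself biases the endpoint. It does not. When dropout is unrelated to these events, similar patients who stay are weighted up correctly (Step 1).

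The documents also give no evidence of selective withdrawal. Protocol 13.2 lets a patient with a second HF admission move to open-label drug but keeps the patient in the trial. Protocol 12.2 asks all subjects to complete assessments through Visit 11 whether or not they stay on study drug. Stopping drug is therefore not leaving follow-up. This stands as an argument about likelihood, but neither passage can retain someone who withdraws consent or is lost.

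Larger effects can be constructed. If 40% of event patients withdraw within 30 days, on top of a 5% background, a difference of about 4.9 days falls to 3.3, a loss of about a third. That scenario takes control-arm dropout to about 11%, against the 5% the protocol expects. The 20-25% figure in protocol 16.2 concerns missing Week 24 NT-proBNP, includes deaths, and is not a dropout rate for this endpoint.

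A reader might also infer that uncoded days after withdrawal count as event-free, since the composite rule calls a day event-free when no component is met. The section on right censoring points the other way. Still, the SAP never defines a patient-level censoring time for the composite, so zero weight is a reasonable inference and not stated text.

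**Conclusion.** The concern holds in a limited form. SAP 10.1 discards days whose value is known, treats other permanent states differently from death without giving a reason, and so relies on an independent-censoring assumption that it does not need. Nothing else in the plan repairs this or would reveal it.

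Bias depends on dropout being more likely after these events. It is upward in each arm's mean, and modest: about 0.4 to 2 days per arm at 5% dropout and HR 3 to 10, up to 4.2 days at 10% dropout. A true difference of about 4.8 days shrinks by about 3% to 10% at 5% dropout, which is small beside a standard error of about 5.3 days. With no true effect, a false difference needs post-event dropout to differ by arm. All sizes rest on assumed event rates and hazard ratios. The change is worth making because it concerns the key secondary endpoint and costs almost nothing.

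**What to change.** In SAP 10.1:

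1. Extend the death rule to every component coded as permanent: second HF admission, LVAD, transplant, and listing unless the SAP states that delisting restores event-free days. *Once any of these occurs, all remaining days through Day 163 are coded 1 and are evaluable, whether or not follow-up later ends.* In sensitivity analysis 1, use Day 168 in place of Day 163.
2. In the Bang-Tsiatis step, set the terminal time to the earliest of death and these events. Count as censored any patient whose follow-up ends before that time and before Day 163 for any reason: withdrawal, loss to follow-up, or the March 1, 2020 data cut. The present component lists do not name that cut.
3. Keep the present rule for ordinary hospital days and inotropes, which are not permanent.
4. State how the composite is coded after the last evaluable date.
5. Keep the current rule as a sensitivity analysis if wanted.

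The cost is a short text change and a small programming change. The event dates are already needed for the daily flags. The fix does not protect against informative dropout before any permanent event; that assumption remains.

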## 10.2 – Secondary Endpoint #2

Endpoint Description: Tolerability measured as number of subjects achieving a target dose of 25%, 50% or 100% of valsartan or LCZ696, using the pre-COVID-19 population.

Response Variable Definition: Due to limited documentation concerning reasons for dose reduction, four versions of this endpoint will be calculated:

- 1) maximum study drug dose started (including 0),
- 2) dose patient took for the most number of days (including 0),
- 3) last dose patient was taking (including 0), and
- 4) last dose patient was taking (excluding 0).

There are 4 ordered values possible based upon the coding of the responses. Each response will be coded to represent 0% of target (no drug), 25% of target (50 mg LCZ696/40 mg Valsartan), 50% of target (100 mg LCZ696/80 mg Valsartan) or 100% of target (200 mg LCZ696/160 mg Valsartan). The number of evaluable days will be based on time from randomization to earliest date of Week 24, Death, Consent Withdrawal, or Last Contact.

Additional Covariates in Addition to Randomized Treatment: atrial fibrillation status at time of randomization

Handling of Dropouts and Missing Data: No adjustment will be made for missing data.

Sensitivity Analysis: Re-calculate the endpoint analysis using the original ITT population.

Statistical Tests: An ordinal logistic regression model (PROC LOGISTIC in SAS) will be used to estimate and statistically compare whether there is differential study drug dose achievement between the treatments.

Interpretation of Treatment Comparison: More patients achieving/tolerating higher doses indicates better tolerance of LCZ696 versus Valsartan.

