10.4 Dosing Guidelines

The study will begin with a 3-7 day run-in period in which all subjects will be administered LCZ696 50 mg po BID. For those subjects taking ACEI prior to the run-in period, the first dose of LCZ696 will be withheld ≥ 36 hours after last ACEI dose. After stopping LCZ696, a 36 hour washout period is required before resuming an ACEI.

Subjects tolerating the LCZ696 in the run-in period will be randomized to either LCZ696 or valsartan. Doses will be assigned in the following fashion:

If previously taking no ACEI/ARB, low-dose ACEI/ARB[†], or eGFR < 30 ml/min/1.73m², ensure ACEI has been discontinued and the last dose was ≥ 36 hours ago, then

- LCZ696 50 mg plus placebo po BID or valsartan 40 mg plus placebo po BID

If previously taking greater than low dose ARB[†]

- LCZ696 100 mg plus placebo po BID or valsartan 80 mg plus placebo po BID*

If previously taking greater than low dose ACEI[†], ensure ACEI was discontinued and the last dose was \geq 36 hours ago, then

- LCZ696 100 mg plus placebo po BID or valsartan 80 mg plus placebo po BID*

* At Investigator discretion, study drug may be started at the low dose (LCZ696/placebo 50 mg po BID or valsartan/placebo 40 mg po BID) if there are any concerns regarding tolerability at the 100 mg / 80 mg dose.

Two weeks after randomization, upward dose titration will occur among subjects tolerating their current dose (SBP > 90 mmHg, creatinine (Cr) \leq 2.0 mg/dL, and no symptoms of hypotension). This will consist of doubling the dose up to a maximum dose LCZ696 200 mg po BID (two 100 mg tablets plus 2 placebo tablets po BID) or valsartan 160 mg po BID (two 80 mg tablets and 2 placebo tablets po BID). For those not tolerating the current dose of study drug, the dose will be down-titrated to the previous tolerated dose.

Two weeks after the prior dose titration visit and four weeks after randomization, further dose titration will occur among subjects tolerating their current dose (SBP > 90 mmHg, Cr \leq 2.0 mg/dL, and no symptoms of hypotension). This will consist of doubling the dose up to a maximum dose LCZ696 200 mg po BID or valsartan 160 mg po BID. For those not tolerating the current dose of study drug, the dose will be down-titrated to the previous tolerated dose. The total duration of study drug treatment will be 24 weeks.

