### 1.2 Study Treatments

Each patient will be randomized to receive either LCZ696 (sacubitril and valsartan) + valsartan-placebo or Valsartan + LCZ696-placebo. Study treatment will be titrated to the target dose of 200 mg LCZ696 as two 100 mg LCZ696 and 2 placebo tablets po BID or to the target dose of 160 mg Valsartan as two 80 mg Valsartan and 2 placebo tablets po BID. Randomized subjects will receive the first dose of study drug as follows:

- For subjects not previously taking an ACE Inhibitor (ACEI) or Angiotensin Receptor Blocker (ARB), previously taking an ACEI or ARB at a low dose, or subjects who have an eGFR < 30 mL/min/1.73m^2, the starting dose of valsartan will be 40 mg po BID and the starting dose of LCZ696 will be 50 mg po BID.
- For subjects taking an ACEI or ARB at greater than low dose, the starting dose of valsartan will be 80 mg po BID and the starting dose of LCZ696 will be 100 mg po BID.

Dose adjustments will be performed every 2 weeks by doubling the dose of LCZ696 or valsartan up to the target maximum dose. The doses of LCZ696 are 50 mg (one 50 mg active and one placebo tablet), 100 mg (one 100 mg active and one placebo tablet) and 200 mg (two 100 mg active and two placebo tablets). The doses of valsartan are 40 mg (one 40 mg active and one placebo tablet), 80 mg (one 80 mg active and one placebo tablet), and 160 mg (two 80 mg active and two placebo tablets).

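### The dose-achievement model in SAP 10.2 omits the starting-dose category, which can cost some power and lets chance imbalance move a tolerability estimate

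*SAP*

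**What the plan says.** Secondary Endpoint #2 codes each patient's dose as 0, 25, 50 or 100% of target: "There are 4 ordered values possible based upon the coding of the responses". SAP 10.2 defines four versions: maximum dose started, dose held for the most days, and last dose with and without zeros. For the analysis, "An ordinal logistic regression model (PROC LOGISTIC in SAS) will be used to estimate and statistically compare" dose achievement between arms. The covariate line reads: "Additional Covariates in Addition to Randomized Treatment: atrial fibrillation status at time of randomization". The section takes more patients at higher doses as better tolerance of LCZ696.

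The starting dose depends on baseline status (SAP 1.2; Protocol 7.3 and 10.4). For patients on no ACE inhibitor or ARB, on a low dose, or with eGFR below 30, "the starting dose of valsartan will be 40 mg po BID and the starting dose of LCZ696 will be 50 mg po BID". For the rest, "For subjects taking an ACEI or ARB at greater than low dose, the starting dose of valsartan will be 80 mg po BID", with LCZ696 at 100 mg. Protocol 10.4 gives the higher group an exception for tolerability concerns: "At Investigator discretion, study drug may be started at the low dose". Doses double at weeks 2 and 4 if tolerated. Protocol 12.2 allows further changes at weeks 8 and 12.

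Randomization is stratified by site and atrial fibrillation (SAP 2.2). SAP 15 lists atrial fibrillation, gender and racial or ethnic minority as subgroups. Starting category appears in neither place.

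**The concern.** The starting category is close to a baseline value of the outcome. A patient who starts at 25% needs two successful doublings to reach target; one who starts at 50% needs one. In the maximum-dose version, a 50% starter who takes drug cannot score 25%. The SAP adjusts for the baseline value of the outcome in 9.1, 11.12 and 11.13, but here it leaves out the nearest equivalent.

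Two things are at stake. Leaving a strong predictor out of an ordinal logistic model lowers power. And because the design does not balance the category, any chance difference between arms passes into the treatment odds ratio and would be read as a difference in tolerance.

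**Working it through.** Neither document gives a power or effect size for this endpoint, so there is no planned figure to reproduce.

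**Inputs from the documents.** Targets are 200 mg LCZ696 and 160 mg valsartan (SAP 1.2). The lower start is 50/200 = 40/160 = 25%; the higher is 100/200 = 80/160 = 50%. The pre-COVID-19 population is 335 (SAP 3), taken as 168 and 167 under 1:1 allocation. Tests are two-sided at 0.05 (SAP 4).

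**Chance imbalance.** The SD of the between-arm difference in the share of 50% starters is sqrt(p(1−p)(1/168 + 1/167)).
- For p = 0.5: sqrt(0.25 × 0.01194) = 0.0546. The 95% range is ±10.7 points; 5 points or more occurs in 36% of randomizations and 10 or more in 6.7%.
- For p = 0.3 or 0.7: SD 0.050, with 32% and 4.6%.

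**How strong could the link be?** Assume, for illustration, that each titration step succeeds independently with probability 0.7 in both categories. A 25% starter reaches target with probability 0.7² = 0.49, a 50% starter with 1 − 0.3² = 0.91. The odds ratio is (0.91/0.09)/(0.49/0.51) = 10.5. This describes maximum dose only.

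**Power.** The proportional-odds model was fitted with and without the category in 3,000 simulated trials per scenario. Assumptions: treatment odds ratio 1.7; atrial fibrillation in 35% with no effect on dose; control-arm shares of 10, 20, 25 and 45% at the four levels for an average starting mix.

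| Category odds ratio | Share starting at 50% | Power, SAP model | Power, category added |
|---|---|---|---|
| 1.5 | 50% | 72% | 73% |
| 3 | 30 / 50 / 70% | 67 / 67 / 67% | 70 / 72 / 71% |
| 6 | 30 / 50 / 70% | 63 / 59 / 59% | 70 / 69 / 69% |
| 10 | 50% | 52% | 67% |

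A two-step titration model of maximum dose, capped at target, with nobody off drug and the 1.7 applied to the odds of success at each step, gave 73% against 87% (control success 0.5) and 57% against 68% (0.7).

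**No treatment effect.** Type I error of the SAP model over six scenarios was 4.8, 5.1, 5.9, 4.8, 5.0 and 4.5%, an average of 30.1/6 = 5.0%. The adjusted model gave 4.6 to 5.3%. Among trials with an imbalance of 5 points or more, the SAP model rejected in 4.0% (odds ratio 1.5), 5.9% (3), 9.2% (6), 9.2% (10) and 7.9 to 8.3% (titration model). The adjusted model rejected in 4.1 to 5.7%.

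**Shift in the estimate.** With no drug effect, 15% off drug and per-step success of 0.4 to 0.7, a 10-point imbalance moves the unadjusted odds ratio for maximum dose to 0.86–0.89 and a 5-point imbalance to 0.93–0.94. Adjusted, it is 1.00.

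**Does proportional odds hold for the new term?** Not exactly, for maximum dose. With 15% off drug and per-step success 0.55:
- Any drug: 0.85 in both categories, odds ratio 1.0.
- At least 50% of target: 0.85 × (1 − 0.45²) = 0.678 against 0.85, odds ratio 5.67/2.11 = 2.7.
- Full target: 0.85 × 0.55² = 0.257 against 0.678, odds ratio 2.11/0.346 = 6.1.

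**The case against.** The strongest reply is that nothing here is invalid. A reader might infer that the comparison is biased or has an inflated error rate. It does not: randomization protects the test, and the simulated error averages 5.0%. The smaller unadjusted odds ratio is non-collapsibility, since marginal and conditional odds ratios are different quantities. Chance imbalance in any unadjusted predictor is already allowed for in the confidence interval. Even the 10-point shift (ln 0.86 = −0.15) is less than one standard error, about 0.20 at this sample size. All of this stands.

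The size can also be challenged. A reader might infer that a loss above 10 points applies to the whole endpoint. The titration model describes maximum dose only. The protocol permits down-titration, later up-titration and dose changes at unscheduled visits, so in the other three versions a 50% starter can score 25%. If tolerated dose is mainly a patient trait, both categories converge. In 500 simulated trials with treatment log-odds 0.5 and no link to last dose, power was 67% without the category and 66% with it; with a weak link (log-odds 0.4) it was 67% and 68%. This stands too.

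A reader might also call this the trial's main measure of up-titration. The documents do not: SAP 6 lists it as one of four tolerability endpoints, with no decision rule. Nor is the SAP uniform on baseline adjustment, since 11.9 and 11.10 list only atrial fibrillation.

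Finally, Protocol 16.1 provides baseline summaries by arm and exploratory analyses to help explain findings. These could show an imbalance, but they do not change the prespecified model.

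**Conclusion.** The point holds as a modest gain in efficiency and interpretability. SAP 10.2 omits a predictor that is fixed before randomization, not balanced by design and likely to be related to at least the maximum-dose version. The test remains valid. The simulated power loss ranges from about 1 point at a category odds ratio of 1.5 to 15 points at 10. The link strength, starting mix, treatment effect and step success rates are all assumptions, because the documents give none of them. Expect the benefit mainly for maximum dose started and little for the last-dose versions. The primary analysis is unaffected.

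**What to change.** In SAP 10.2, add the protocol starting-dose category to the ordinal models alongside treatment and atrial fibrillation: ACE inhibitor or ARB none or low dose, or eGFR below 30, versus ACE inhibitor or ARB above low dose. Derive it from pre-randomization data. Do not use the dose actually started, because Protocol 10.4 lets investigator judgement enter it and a patient who takes no drug has none.

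State that the reported odds ratio is conditional on the covariates. Check proportional odds for the added term, and use a partial proportional-odds model if it fails. Tabulate dose achieved by arm within each category.

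The cost is one covariate, one check, one table and an odds ratio with a slightly different meaning. The dosing rule already requires the baseline data.
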